3.3 Study measurements

To begin with, possible participants will be screened for eligibility before inclusion. First, patients with long COVID symptoms can be referred after completing the screening tests, assessing psychological and cognitive complaints, and can be included if these self-report questionnaires indicate neuropsychiatric symptoms. The control group will perform a screening test to exclude any self-reported psychological or cognitive complaints. If possible, these screening tests will be organized on an online platform.

The data which will be collected for this study which are part of routine clinical practice include the following procedures:

- a baseline clinical psychiatric interview to determine a patient's past and current mental state and psychiatric diagnosis, including psychiatric rating scales
- a baseline neuropsychological evaluation including a standardized test battery (optional)
- extensive neurocognitive tests to examine and document persistent cognitive complaints

Additionally, the following study-related procedures will be performed:

- informed consent and eligibility screening
- blood sample draw (max 35ml per visit)
- saliva cortisol sampling
- additional self-rated scales assessing insomnia, fatigue and psychopathology
- a questionnaire regarding important bio-psycho-social factors such as familial psychiatric antecedents, socio-economic status, social network during the pandemic, personal experience with the COVID-related restrictions, ...

3.3.1. Psychiatric interview

The psychiatric interview will be performed at baseline by the treating physician as part of standard clinical practice and will include diagnostic evaluation using the MINI. **If the MINI was not yet performed by the treating physician, this will be performed during the screening.**

Validated self-report questionnaires will be used to assess psychopathology on each time point of the study (see table 1).

Table 1: Neuropsychiatric rating scales

Domain	Scale		Cut-off
SCREENING PHASE (before inclusion)			
Depression, anxiety, trauma	RMT-20	Rapid Measurement Toolkit 20 (40)	MDD \geq 13 GAD \geq 11 SAD \geq 12 Panic \geq 9 PTSD \geq 8
Depression	BDI-21	21-item Beck depression inventory (41)	10-18: mild 19-29: moderate 30-63: severe
Anxiety	STAI	State-Trait Anxiety Inventory (42)	State: \geq 39
Trauma	PCL-5	PTSD Checklist for DSM-5 (44)	\geq 33
	IES-R	Impact of Event Scale - Revised (45,46)	\geq 33
Insomnia	ISI	Insomnia Severity Index (47)	\geq 10
Neurocognitive	CFQ	Cognitive Failure Questionnaire (subjective) (48)	General cut-off score of \geq 43.
IQ	RSPM-SF	Raven Standard Progressive Matrices (Short Form) (39)	IQ $>$ 90
Substance abuse	ASSIST	Alcohol, Smoking and Substances Involvement Screening Test (72, 73)	\geq 11 for alcohol, \geq 4 for other substances
COVID-19	C19-Re habNe q	COVID-19 Rehabilitation Needs Questionnaire (70)	No cut-off
CLINICAL/EXPERIMENTAL PHASE (baseline – T1 – T2 -T3)			
Diagnosis (only baseline)	MINI	Mini International neuropsychiatric Interview (49)	
Depression	HDRS-17	17-item Hamilton Depression Rating Scale	8-13: mild 14-18: moderate 19-22: severe \geq 23: very severe
	BDI-21	21-item Beck depression inventory (41)	
Anxiety	STAI	State-Trait Anxiety Inventory (42)	
Insomnia	PSQI	Pittsburgh Sleep Quality Index (50)	\geq 5
	ISI	Insomnia Severity Index (47)	

	DRFS	Dream recall frequency scale (exp) (51)	
	ITI	Insomnia Type Inventory (exp)	(only if ISI >9)
Fatigue	FSS	Fatigue Severity Scale (52)	
Trauma	CTQ	Childhood trauma questionnaire (53)	
	IES-R	Impact of Event Scale - Revised (45,46)	≥33
Neurocognitive	DSC	Digit Symbol Coding Subtest from WAIS-IV	see 3.3.2.
	CWI	Color Word Interference Test from the Delis-Kaplan Executive Function System	see 3.3.2.
	BWT	Bourdon-Wiersma Test	
	DS	Digit Span Subtest from WAIS-IV	see 3.3.2.
	RAVLT	Rey Auditory-Verbal Learning Test	see 3.3.2.
	CFT-R	Complex Figure Test (Rey figure)	see 3.3.2.
	BNT-SF	Boston Naming Test, short form	see 3.3.2.
	COWA T	Controlled Oral Word Association Test	see 3.3.2.
	WFT	Word Fluency Test	see 3.3.2.
	S MR	Subtests Similarities from WAIS-IV Subtest Matrix Reasoning from WAIS-IV	see 3.3.2.
	TOL	Tower of London	see 3.3.2.
	TMT	Trail Making Test from the Delis-Kaplan Executive Function System	see 3.3.2.
	PPT	Purdue Pegboard Test	see 3.3.2.
Substance abuse	ASSIST	Alcohol, Smoking and Substances Involvement Screening Test (72, 73)	
COVID-19	PCFS	Post-COVID-19 Functionele Statusschaal (71)	No cutoff

3.3.2. Neuropsychological assessment

COVID-19 patients with persistent complaints of cognitive disabilities (more than 4 weeks post-infection) in daily life are examined with an extensive neuropsychological test battery (see below) at the outpatient clinic of the University Psychiatric Centre in Duffel and at the University Hospital Antwerp. This battery covers a broad range of reliable and valid tests divided into six cognitive domains: attention, memory, visuospatial functions, language, executive functions and psychomotor speed/coordination. The neuropsychological examination lasts an average of 2 hours per participant. The tests are carried out by the

same experienced neuropsychologist and also follow a standardized sequence. In addition to the neuropsychological assessment, two self-report scales are filled out by each patient. These scales are used to detect possible complaints of fatigue and possible cognitive problems which are experienced by the patient during daily life activities.

A control group of on average 50 COVID-19 survivors without persistent complaints (Ca), matched on age and years of education with the patient group, will also undergo the neuropsychological test battery.

- *Attention*
- The Bourdon-Wiersma Test (BWT) (54) was used to evaluate sustained attention. The primary outcome variables are mean rule time and total omissions.
- The Digit Symbol Coding Subtest from the Wechsler Adult Intelligence Scale (4th Edition) (WAIS-IV (DSC)) (58) is used to assess divided attention and speed of information processing. The total correct symbols and the total errors (or incorrect symbols) within the allowed time of 120 s are used as outcome measures.
- The Dutch version of the Color Word Interference Test from the Delis-Kaplan Executive Function System (D-KEFS (CWI)) (65) is administered to measure focused attention and inhibition of interference (card III) and alternating attention and cognitive flexibility (card IV). The total raw score (total time) and the total uncorrected errors for card III (evaluation of focused attention) and card IV (evaluation of alternating attention) are used as outcome measures
- *Memory*

The Digit Span Subtest from the Wechsler Adult Intelligence Scale (4th Edition) (WAIS-IV (DS)) (58) is used to evaluate working memory. For the digit span forward and the digit span backward we use the total raw score and the longest span (forward or backward) as outcome measures.

The Rey Auditory-Verbal Learning Test (RAVLT) (54,55) is administered to evaluate auditory-verbal memory for unrelated information. The variables we use for the analysis are total immediate recall (over 5 trials) (the maximum learning score is 75), long-term delayed recall (after a 20-min time interval; the

maximum recall score is 15) and long-term delayed recognition (after a 20-min time interval; the maximum recognition score is 15).

Visuospatial memory for related information is assessed by means of the Complex Figure Test (Rey figure) (CFT-R) (54–56). The two measures we use are immediate recall and long-term delayed recall (after a 20-min time interval) of recently learned information.

- *Visuospatial functions*

The copy of the Complex Figure Test (Rey figure) (RCFT-R) (54–56) is administered to evaluate visuospatial judgement. The total score (with a maximum of 36) is recorded.

- *Language*

In our study we administer the short form of the Boston Naming Test (BNT-SF) (66) to measure word finding (i.e., naming of 29 objects). The outcome measure is the total correct answers (with a maximum of 29).

- *Executive functions*

The Controlled Oral Word Association Test (57) and the Word Fluency Test (WFT) (67) are used to assess phonetic verbal fluency and semantic verbal fluency, respectively. The total words generated is used as outcome measure for both tests.

The Subtests Similarities and Matrix Reasoning from the Wechsler Adult Intelligence Scale (4th Edition) (WAIS-IV (S) and WAIS-IV (MR)) (58) are selected to measure verbal abstract reasoning and non-verbal abstract reasoning, respectively. The total raw score is used as outcome measure for both subtests.

The Tower of London Test (59) is used to evaluate planning and problem solving. The outcome variables are the total correct score, the total move score and the total problem-solving time.

- *Psychomotor speed/coordination*

The conditions 4 and 5 of the Trail Making Test from the Delis-Kaplan Executive Function System (D-KEFS (TMT)) (68) are administered to evaluate psychomotor speed with a cognitive component (cognitive flexibility) (condition 4) and psychomotor speed without a cognitive component (condition 5). For both conditions, the total raw score (total time) is used as outcome measure.

The Purdue Pegboard Test (60) is used to assess psychomotor coordination. The total raw score (or the average of three trials, each trial with a time limit of 30 s) for the preferred hand, for the

non-preferred hand and for both hands are used as outcome measures.

- *Cognitive functioning in daily life*

The Cognitive Failure Questionnaire (CFQ) (69) is used to detect possible cognitive problems (or failures) which are noticed by patients during daily life activities in the past four weeks. This self-report scale consists of 25 items with a rating of 0 (never), 1 (rarely), 2 (sometimes), 3 (often) or 4 (very often) for each item. The total score (with a maximum of 100) is used as outcome measure.

- *Fatigue*

The Fatigue Severity Scale (FSS) (61) is used to detect possible complaints of fatigue in daily life by the patient. This self-report scale consists of 9 items about fatigue, its severity and how it can affect several daily activities. The items are scored on a 7-point rating scale from 1 (strongly disagree) to 7 (strongly agree). The total score is used as outcome measure (with a maximum of 63).

- Cognitive rehabilitation

The COVID-19 patients are divided into two groups: a treatment group and a non-treatment group. The patients in the treatment group follow a cognitive rehabilitation program. This program consists of 12 group sessions of one hour (one session per week). A maximum of 6 patients participate to a group session. Each session consists of two cognitive rehabilitation methods. These are restorative therapy (which means administering several cognitive exercises (with increased level of complexity) in order to improve the specific cognitive deficits of each individual patient (as was detected by means of the neuropsychological baseline evaluation) with regard to attention, memory and/or executive functions) and (2) compensatory therapy (which means teaching compensation strategies in order to cope better with the cognitive disabilities concerning attention, memory and/or executive functions that each individual patient experiences during daily life activities). The patients in the non-treatment group receive no cognitive rehabilitation program.

- Neuropsychological reassessment

The patients in both groups (treatment group versus non-treatment group) undergo a neuropsychological reassessment after approximately 3 months. For some tests (RAVLT, CFT-T (Taylor figure), COWAT and WFT) a parallel

version is used to minimize a possible practice effect. Of course, for the treatment group this neuropsychological reassessment is necessary to evaluate the progression of cognitive functioning after 3 months of cognitive rehabilitation.

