Also, long COVID can be regarded as a condition of chronic stress, which could theoretically be associated with disturbances of the hypothalamo-pituitary-adrenal (HPA) axis, although no studies on HPA axis (dys)function in long COVID have been reported yet.

The aims of this study are to describe the standardized evaluation of the psychopathological and neurocognitive function of long COVID patients and their evolution over time; to explore the cross-sectional and longitudinal association

between long COVID symptoms and immunological measures; and to examine the neuro-endocrine (HPA-axis) characteristics of long COVID syndrome.

Three participant groups will be included: 1) long COVID patients with neuropsychological complaints (P), 2) COVID-survivors without persistent complaints (Ca) and 3) healthy volunteers (Cb).

This is a longitudinal study, starting from November 1st 2021. Enrollment will continue for an estimated period of 24 months, depending on the time course of the epidemic curve. Last-patient-in is expected no later than November 1st, 2023. The study will be organized into three work packages (WP1, WP2 and WP3). WP1 includes psychiatric assessments using questionnaires and blood sampling and is the standard WP for every participant. WP2 includes cortisol measurement using saliva sampling for patients and controls from Cb. who do not fulfill specific exclusion criteria (pregnancy, breastfeeding, hormonal therapy with exception of contraceptives, cortisol treatment). Finally, WP3 includes an extensive neurocognitive assessment by a specialized neuropsychologist for both patients and controls from Ca who do not fulfill specific exclusion criteria (sedative medication, pre-existing neurological disease, severe substance abuse, and IQ < 90).

Patients and controls from Ca will be referred mainly by the University Hospital of Antwerp (UZA) and by long COVID patient support groups and enrolled at first visit to UPCD, where follow-up will also take place at 3, 6 and 12 months. WP1 will be performed at each timepoint, while WP2 and WP3 will only be carried out at baseline and 6 months.

Total sample size is estimated on 130 participants.

List of Abbreviations

- ACTH: adrenocorticotrophic hormone
- BACS: brief assessment of cognition in schizophrenia
- BDI: Beck depression index
- Ca: Control group a: COVID-survivors without NP complaints
- CAR: cortisol awakening response
- Cb: Control group b: healthy controls
- CFS: chronic fatigue syndrome

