1.2. Neurocognitive deficits following COVID-19

Memory and attention problems, reduced information processing and executive dysfunction are among the most frequent complaints of long COVID patients. Specific complaints include concentration difficulties, mental exertion, word finding difficulties, problems with both explicit and procedural memory retrieval (i.e. difficulty completing tasks which used to be "automatic") and problems with planning and organization of daily activities, combined with the subjective experience of "brain fog" (7,15–17).

Scientific evidence is indicating these cognitive deficits are alarmingly widespread among COVID-survivors. In a longitudinal cohort study of 130 Italian patients aged 18-70 years who were assessed with the Brief Assessment of Cognition in Schizophrenia (BACS) (18) at one and three months after acute COVID-19 pneumonia, only 25 patients (19%) showed equivalent scores within the normal range in all cognitive domains (i.e., verbal memory, verbal fluency, working memory, selective attention, processing speed, psychomotor coordination and planning and problem solving), whereas 21 (16%) were poor performers in at least one function, 22 (17%) in two, 18 (14%) in three, 14 (11%) in four, 7 (5%) in five, and 2 (1.5%) demonstrated deficits in all domains (7).

In the study carried out by Miskowiak et al. (17) cognitive functioning was assessed in a group of 29 Danish COVID-patients approximately three to four months after hospitalisation by means of the Screen for Cognitive Impairment in Psychiatry (SCIP) and the Trail Making Test. Fifty-nine % of the patients showed cognitive deficits (38% was globally impaired and 21% was selective impaired), with verbal memory and executive functions being most affected. Ortelli et al. (16) investigated cognitive functions by means of the MOCA, the FAB and three computerized attentive tasks (the vigilance task, the Stroop interference task and the Navon task) in a group of 12 Italian COVID-survivors approximately 9 to 13 weeks from onset of infection. In comparison with a healthy control group, the patient group showed a significant reduced global cognitive functioning (MOCA and FAB) and significant more problems with vigilance and executive attention (computerized attentive tasks).

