Based on current referral rates, we expect on average 1-2 new referrals each week. After 12 months, we expect a total of ± 50 patient inclusions. In a MANOVA analysis, a total sample size of 64 offers 80,0% power to detect a medium sized effect ($f^2 \geq 0.15$). We aim for a total sample size of 130 in order to achieve higher effect sizes and to maintain sufficient power in the subgroup analyses and in case of missing values. As Ca is the main control group for the long COVID patient group, these two groups are of equal size (both 50 participants). We included a smaller Cb group to compare the immunological blood parameters between healthy volunteers and long COVID patients.

Study visits:

As part of routine clinical care, patients will receive psychiatric evaluation at the University Hospital Campus UZA, and neurocognitive evaluation at Campus Duffel. During the clinical evaluations, participants will be invited to participate in the study. If they are interested, they will be invited to a baseline visit assessing eligibility and covering informed consent procedure. In order to adhere to social distancing regulations, it may occur that this baseline visit is held digitally via livestream/webcam or by telephone. In this case, patients sign their ICF digitally. To ensure patient privacy, only in-house fully secured internet and telephone connections will be used for distanced baseline visits.

Once included, the participant will be invited for the baseline assessment, which includes a broad neuropsychological examination. A blood sample will be collected at each time point during the study.

	SCREENING	BASELINE	3 MONTHS	6 MONTHS	12 MONTHS
PATIENT GROUP	Eligibility, psychiatric and IQ screening	Psychiatric assessment Blood sample	Psychiatric assessment Blood sample	Psychiatric assessment Blood sample	Psychiatric assessment Blood sample
+ NC SUBGROUP		Neurocognitive assessment		Neurocognitive assessment	
+ HPA SUBGROUP		Saliva sample		Saliva sample	
CONTROL GROUP A	Eligibility, psychiatric and IQ screening	Psychiatric assessment Blood sample	Psychiatric assessment Blood sample	Psychiatric assessment Blood sample	Psychiatric assessment Blood sample
+ NC SUBGROUP		Neurocognitive assessment			
+ HPA SUBGROUP		Saliva sample			

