3.4. Endpoint measurements

“NP symptoms”

- Baseline and follow-up scores on clinical scales of depression, anxiety, and insomnia
- (subgroup) Baseline and follow-up cognitive functioning

“Inflammation”

- Quantitative measurement of HERV-W-ENV in serum at baseline
- Calculation of systemic immune inflammatory index (SII= thrombocyte count x neutrophile count / lymphocyte count) at baseline and follow-up
- Quantitative analysis of CRP and IL-6 at baseline and follow-up
- Quantitative analysis of kynurenine metabolites at baseline and follow-up

(subgroup) *“HPA axis”*

- CAR

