3.5. Statistical analysis

CAPRI has ongoing collaborations with StatUA and BIOMINA for statistical analyses of past and ongoing projects involving biomarker-data. In this project, we will study cross-sectional and bidirectional longitudinal associations between *NP symptoms* and *Inflammation* or *Insomnia* (cfr above).

To study the cross-sectional association using all available data, we will stack data from all timepoints in one cross-sectional dataset. To account for the fact that one person can have multiple observations in this combined cross-sectional dataset, we will analyze the association between NP symptoms and inflammation / insomnia (measured at the same timepoint) using linear mixed models with timepoint as repeated effect and patient identifier as within-subject effect and using an unstructured correlation matrix. Estimates from this model thus represent the cross-sectional association between predictor and outcome.

For longitudinal analyses the effect of baseline *Inflammation* and *Insomnia* on *NP symptoms* at 3- and 6-month follow-up will be evaluated using linear mixed models with time as repeated effect and patient identifier as within-subject effect and using an unstructured correlation matrix. Baseline predictor by time interaction (time coded as 0, 3, or 6) will be included to test differences in slope but retained only in models when statistically significant. Treatment group (antidepressant treatment, insomnia treatment, cognitive remediation, a combination, or none) will be included

as predictor. Baseline values of NP symptoms will be included as covariates, and all other covariates measured at baseline as well.

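### Digit Symbol Coding errors are a raw count in a fixed 120 s, so if patients are slower their accuracy deficit is understated

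*Combined protocol and SAP*

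**What the plan says.** Section 3.3.2 (Attention) gives the DSC two outcome measures: "The total correct symbols and the total errors (or incorrect symbols) within the allowed time of 120 s are used as outcome measures". The same paragraph says that the test "is used to assess divided attention and speed of information processing". No error rate, percentage accuracy or number of symbols attempted is defined there.

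Later sections do not supply one. Section 3.4 lists the cognitive endpoint for the subgroup only as "Baseline and follow-up cognitive functioning". Section 3.5 plans "linear mixed models with timepoint as repeated effect and patient identifier as within-subject effect" and mentions neither an offset nor an adjustment for symbols attempted. It does not name DSC errors.

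On speed, section 1.2 reports that "reduced information processing and executive dysfunction are among the most frequent complaints of long COVID patients", without giving a size.

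**The concern.** The two DSC scores are meant to show different things: how fast the participant works and how accurately. A raw error count within a fixed time does not isolate accuracy. Everyone gets the same 120 s, but not the same number of opportunities to err. Opportunities depend on speed, which this test is also used to measure.

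The protocol gives reason to think that speed may differ between patients (P) and Ca, the main contrast. If it does, the error comparison is shifted towards fewer errors in patients. Equal accuracy then looks like a patient advantage, and a real deficit looks smaller than it is.

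Reassessment has the same problem. A participant who speeds up at unchanged accuracy makes more errors. The parallel versions that 3.3.2 provides against practice effects cover the RAVLT, the complex figure, the COWAT and the WFT, but not the DSC. A gain in DSC speed from practice or recovery is therefore possible, and the raw count would then show it as more errors.

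**Working it through.** **The plan's own figure.** The documents give no expected number of attempts, error rate, SD or power for DSC errors, so there is nothing to reproduce. The only power statement ("a total sample size of 64 offers 80,0% power to detect a medium sized effect") refers to a MANOVA and has no bearing on this score.

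**Inputs from the documents.** Time limit 120 s and two raw counts (3.3.2). Planned group sizes are 50 P and 50 Ca (sample-size paragraph), before the exclusions for neurocognitive testing.

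**Inputs that are assumptions.** Control attempts with mean 75 and SD 12; control error probability 1–4% per symbol; between-person coefficient of variation (CV) of the error probability 0.5–1.0; patients 5%, 10% or 20% slower.

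**Step 1: formula.** Attempted = correct + errors. Expected errors = attempted × error probability. Hence

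count ratio (P/Ca) = speed ratio × error-rate ratio.

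The raw counts are equal when the error-rate ratio is 1/(speed ratio):

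- 5% slower: 1/0.95 = 1.05
- 10% slower: 1/0.90 = 1.11
- 20% slower: 1/0.80 = 1.25
- 30% slower: 1/0.70 = 1.43

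Below that value a true deficit is reversed, at it the deficit is hidden, and above it the deficit is attenuated.

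**Step 2: worked example.** Controls: 75 × 0.04 = 3.00 expected errors. Patients 20% slower attempt 75 × 0.80 = 60 symbols.

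| True error-rate ratio | Patient errors | Count ratio | Reading of the raw count |
|---|---|---|---|
| 1.0 | 60 × 0.040 = 2.40 | 0.80 | false patient advantage |
| 1.1 | 60 × 0.044 = 2.64 | 0.88 | deficit reversed |
| 1.25 | 60 × 0.050 = 3.00 | 1.00 | deficit hidden |
| 1.5 | 60 × 0.060 = 3.60 | 1.20 | deficit attenuated |
| 2.0 | 60 × 0.080 = 4.80 | 1.60 | deficit attenuated |

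**Step 3: retest.** A participant who moves from 60 to 75 attempts at a constant 4% goes from 2.40 to 3.00 expected errors. That is a rise of 75/60 − 1 = 25% with no change in accuracy.

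**Step 4: effect on the test.** Simulation of 50 v 50, 4000 runs per scenario, with binomial errors and gamma-distributed personal error rates. Two-sided 5% t-tests were run on the raw count and on errors/attempted. Ranges run over error rates of 1–4% and CVs of 0.5–1.0.

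| Slowing | Equal accuracy: raw count significant | Equal accuracy: rate significant | 1.5-fold error rate: power, raw count | 1.5-fold error rate: power, rate |
|---|---|---|---|---|
| 5% | about 5–6% | about 5% | – | – |
| 10% | about 5–11% | about 5% | about 16–50% | about 26–78% |
| 20% | about 10–28% | about 5% | about 10–21% | about 25–76% |

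At 20% slowing nearly all the false-positive results point to fewer errors in patients. The upper ends belong to the 4% error rate with CV 0.5. At low error rates and high CV, power is poor under either scoring.

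**The case against.** The strongest reply has four parts.

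*The denominator is not lost.* Both counts are planned outcomes, so attempted = correct + errors is available for every participant, and any slowing shows in total correct. This is true, and it is why the fix is cheap. It does not answer the point, because the plan names the raw count as the outcome. Reading a second score beside it does not correct the error comparison or its p-value.

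*Slowing is not shown.* Section 1.2 describes complaints, not measured DSC speed. Section 1.2 also reports that psychopathology affected information processing in post-COVID patients, but again without a size. This stands: the bias between P and Ca is conditional on a speed difference that the documents make plausible but do not quantify.

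*The effect may be small.* At 5% slowing the raw count behaves almost nominally. At a 1% error rate the score is weak however it is analysed. The simulation also draws speed and error rate independently, so it ignores a speed–accuracy trade-off. All of this stands, and it is why ranges are given.

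*The score matters little.* DSC errors are one of two scores on one test, in a battery of more than a dozen tests given to a subgroup. No sample-size figure rests on them. This stands and sets the severity.

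A reader might infer that an accuracy deficit in patients will be hidden or reversed as a matter of course. The documents do not support that. They report no DSC accuracy deficit, and hiding or reversal needs an error-rate ratio at or below 1/(speed ratio).

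**Conclusion.** The point holds in conditional form. As written, the DSC error outcome mixes accuracy with speed. The direction of the bias follows from arithmetic alone: if patients are slower, the comparison is shifted towards fewer patient errors and any true deficit is attenuated. Whether it goes as far as hidden or reversed depends on ratios that the documents do not give. Likewise, a participant who speeds up shows more errors only if per-symbol accuracy is unchanged or improves by less than speed.

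The size ranges from negligible at 5% slowing to material at 20%, where false-positive rates reach about 10–28% and power for a 1.5-fold error rate falls from about 25–76% to about 10–21%. These figures rest wholly on assumed attempts, error rates and CVs. Severity is low: this is an inexpensive improvement to one secondary score, not a threat to the study's main conclusions.

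**What to change.** In section 3.3.2, replace total errors as a DSC outcome by errors per symbol attempted, errors / (correct + errors). Keep total correct symbols as the speed outcome.

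State the model in section 3.5: an overdispersed binomial, or a count model with log(symbols attempted) as offset, with a person-level random effect where repeated visits are analysed. Fix the choice before the data are examined. The raw error count can still be tabulated descriptively beside the number attempted.

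The cost is a sentence in each section. Both counts are already recorded, so no new data or change in test administration is needed. The one small downside is that this score needs a different model from the linear mixed models planned elsewhere. The rate does not remove a deliberate speed–accuracy trade-off, so it should be reported together with total correct.
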